6.1.3 Product Storage and Stability

The final Investigational Product will be injected intralesionally within four hours of the final formulation at the pharmacy. A more comprehensive product stability assessment will be part of this Phase 1 study.

6.1.4 Preparation

Described below is the preparation of IFx-Hu2.0 Investigational Product intralesional injection using a vaccine kit that contains; (1) Vial 1-pDNA (drug substance), (2) Vial 2- cationic polymer (excipient), and (3) Vial 3-glucose (excipient). These components will be provided by Morphogenesis to the Pharmacy for mixing on site as per USP <797> guidelines for single-dose containers. When possible, the preparation should be performed in an ISO 5/Class 100 environment. The vaccine kits are stored at 2-8°C until preparation is performed. All components will have accompanying Certificates of Analysis.

1. Incubate kit at room temperature (RT) for 30-60 minutes prior to mixing
2. Place mixed final product label, provided in Bag 1 of kit, on Vial 1
3. Remove flip cap from vials, wipe the exposed septum with alcohol as per standard clinical pharmacy procedures, and then draw up 0.1 mL of Vial 3 into a ½ mL tuberculin (TB) syringe

[figure not shown]
provided with kit

4. Place Vial 1 upright on a flat surface, and using aseptic technique, insert needle and inject Vial 3 solution into Vial 1, before removing the needle pull back on the syringe to release any pressure
5. Using a new ½ mL TB syringe, provided with kit, draw up 0.2 mL of Vial 3 and inject solution into Vial 2 using the same technique described in Steps 3 & 4
6. Vortex Vial 1 & Vial 2 individually at the “8” setting for five seconds, if this step is performed outside of the ISO 5 environment wipe vial septum with alcohol as performed in Step 3

Note: This is a CRITICAL step to ensure complexes form properly

7. Using a new ½ mL TB syringe, provided with kit, draw up 0.2 mL of Vial 2 and inject contents into Vial 1 using the same technique described in Steps 3 & 4
8. Gently vortex Vial 1 using the same technique described in Step 6
9. Allow to incubate at room temperature for 15 minutes; the mixed solution is stable for 4 hours at room temperature after components are combined
10. The final drug product is now ready for intralesional administration using a TB syringe, supplied at the clinical pharmacy, at a dose of 0.2 mL/lesion
11. The used vials should be placed in the designated biohazard bag, provided in the kit, and returned to Morphogenesis

Steps 1 & 2
Incubate kit at RT for 30-60 minutes & then place final product, IFx-Hu2.0, label on Vial 1 before mixing

6.1.5 Dosing and Administration

The target dose will be 100 µg of plasmid DNA per lesion injected at a final dose volume of 0.2 mL per lesion. The maximum number of lesions to be injected at any given time point in the study phase proposed is three lesions.

6.1.6 Route of Administration

Intralesional injections using 1 mL tuberculin syringes.

6.1.7 Starting Dose and Dose Escalation Schedule

The dose/lesion treated will be constant through this study: 100 µg of plasmid DNA per lesion injected at a final dose volume of 0.2 mL. However, depending on the subject, one, two, or three lesions would be injected at a time.

The subjects will receive IFx-Hu2.0 at a single time point as a monotherapy. These patients will then be observed for any dose-limiting toxicity or adverse events for up to four weeks. The maximum number of lesions to be injected in this study is three lesions.

6.1.8 Dose Adjustments/Modifications/Delays

No dose adjustments or modifications will be part of this study phase. However, the protocol will allow for delays of up to 7 business days to accommodate participant clinic visit rescheduling due to any unforeseen circumstances.

6.1.9 Duration of Therapy

Participants enrolled in the study will receive IFx-Hu2.0 at a single time point. After primary endpoint has been met (DLT), at the investigator's discretion in consultation with the sponsor, patients may receive additional doses on a 3-week cycle.

6.1.10 Tracking of Dose

Once the final Investigational Product is formulated, patient-specific labeling will be affixed showing two unique identifiers.

6.2 Study Agent Accountability Procedures

The final Investigational Product mixing involves the drug substance (pAc/emm55 plasmid DNA in TE buffer) with the remaining components; cationic polymer and glucose. This mixing of the final Investigational Product components will occur at the clinical site pharmacy. Once the final Investigational Product is prepared, patient-specific labeling will be affixed showing two unique identifiers. Any excess product will be de-identified and returned to Morphogenesis for laboratory studies.

7 STUDY PROCEDURES AND SCHEDULE

7.1 Study Procedures/Evaluations

7.1.1 Study-specific Procedures

- Medical history through interview and/or medical records review
- Medication history to include current prescription and over-the-counter medications; a review of current medications will be part of the assessment of eligibility
- Physical examination
- Radiographic or other imaging assessments (photographs)
- Biological specimen collection and laboratory evaluations; blood draws and urine collections will be made at each of the clinical visits in addition to tissue tumor tissue collection for research purposes.
- A discussion of the results of any study-specific procedures will be provided to the participant
- Assessment of adherence to study requirements and instructions
- Collection of data on gender, race and ethnicity

7.1.2 Standard-of-care Study Procedures

Subjects will receive IFx-Hu2.0 as a monotherapy at a single time point and will be assessed for a period of four weeks. Once the four-week period expires and the toxicity/safety assessments have been completed, these patients will transition into standard-of-care or clinical trial protocols as determined by the PI and the clinical team. If the patient comes off study, PFS will need to be censored, but the time to first progression will be obtained during subsequent follow-up with the patient's consent. If the patient has a response to therapy, the patient will have the option of continuing the study at three-week intervals at the discretion of the PI in consultation with the Sponsor. In this setting, PFS will be measured in the traditional way. Where feasible, as determined by PI, tumor biopsies and peripheral blood collections may be obtained on subsequent treatment cycles.

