The trial will be conducted in accordance with the ICH E6, the Code of Federal Regulations on the Protection of Human Subjects (45 CFR Part 46). The Principal Investigator will assure that no deviation from, or changes to the protocol will take place without prior agreement from the sponsor and documented approval from the Institutional Review Board (IRB), except where necessary to eliminate an immediate hazard(s) to the trial participants. All personnel involved in the conduct of this study have completed Human Subjects Protection Training.

I agree to ensure that all staff members involved in the conduct of this study are informed about their obligations in meeting the above commitments.

Principal Investigator: _____

[figure not shown]
Signature: _____ Date: _____

PROTOCOL SUMMARY

Title	Phase 1 Study Using a Plasmid DNA Coding for Emm55 Streptococcal Antigen in Patients with Unresectable Stage III or Stage IV Cutaneous Melanoma
Short Title	pDNA Intralesional Cancer Vaccine for Cutaneous Melanoma
Protocol Number	Melanoma 2017-01
Phase	Phase 1
Methodology	Non-randomized, open-label, uncontrolled
Study Duration	Approximately 1 year
Study Center(s)	Single-center
Objectives	Primary: To assess safety and feasibility Secondary: To assess any antitumor response
Number of Subjects	Six
Diagnosis and Main Inclusion Criteria	Male or female, confirmed stage III or stage IV unresectable melanoma with lesions accessible for intralesional injection
Study Product, Dose, Route, Regimen	Plasmid DNA encoding a Streptococcal antigen in a cationic polymer-based solution in doses of 100 µg delivered intralesionally at a single time point “Week 0” with a maximum of three lesions injected. The primary endpoint (DLT) will be assessed at 4 weeks.
Optional dosing	After primary endpoint has been met (DLT), at the investigator’s discretion in consultation with the sponsor, patients may receive additional doses on a 3-week cycle.
Follow-up - Primary	Week 4; Day 28+/-7 business days.
Follow-up – Optional.	21 days +/- 7 business days from last dose administered.
Follow-up – Long-term	Obtain OS/subsequent treatments for melanoma after MCC 19500 as of 11/16/2020 for all patients with clinical response if available.

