Study Procedures	
Six patients will receive IFx-Hu2.0 on an outpatient basis at a single time point in a single lesion, two lesions, or three lesions, as a monotherapy (a maximum of three lesions could be injected). These patients will be assessed for any immediate adverse reactions and at Week 4 (Day 28+/-7 business days) for any delayed adverse events.
 
After the primary endpoint has been met (DLT), patients may receive additional doses on an optional 3-week cycle.

Duration of Administration	Single time point with option for additional doses
Potential Risks	Other cancer vaccine trial results have reported patients experiencing reactions such as mild fever, skin reactions, sweats and chills, which are often described as “flu-like” symptoms.
Reference Therapy	None

Statistical Methodology	The data analysis is described to assess the safety of the injection of the study agent in six patients. The intention-to-treat approach will be used for response to treatment data analysis of this trial (secondary objective). The exploratory testing will be mainly descriptive in this pilot set of patients
--------------------------------	---

SCHEMATIC OF STUDY DESIGN

Note: If patient consents to additional treatment, this may be performed every three weeks with a 21-day follow-up visit.

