Enrollees will receive IFx-Hu2.0 at a single time point. Depending on the number of accessible lesions, a patient could receive up to three doses across three lesions (one dose per lesion). Forty milliliters of peripheral blood will be collected from these patients prior to treatment administration and at the follow-up visit four weeks later. The target dose will be 100 µg of plasmid DNA per lesion injected at a final dose volume of 200 µL per lesion. To allow for the observation of any acute toxicity in the first subject enrolled and prevent any occurrence of excessive toxicities in subsequent subjects, the first subject enrolled will receive a single dose of IFx-Hu2.0. Subsequent subjects will be administered the product after at least seven days. Beyond the first subject, the maximum number of lesions to be injected at any given time point in the study phase proposed is three lesions. These samples will be used to perform complete blood counts (CBC) and clinical chemistry tests. A urine sample will be obtained for urinalysis for protein and blood at the same frequency. Blood samples will be drawn for immune response evaluation as well. Peripheral blood collections, and where feasible, as determined by PI, tumor biopsies may be obtained on the first and subsequent treatment cycles. At the end of the study period a biopsy of the lesion injected and a non-injected lesion (if applicable) will be collected. At the discretion of the PI in consultation with the Sponsor, the patient will have the option of continuing the study at three-week intervals so long as the subject under study has not progressed.

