7.3.4 Final Study Visit

(Week 4 Day 28 +/- 7 business days for Single Dose Cycle)

OR

(Week 21 +/- 7 business after the last dose for Multiple Dose Cycle)

- Record vital signs, results of physical examination
- Collect blood/urine for:
 - Hematology: CBC - hemoglobin, hematocrit, white blood cells (WBC) with differential count, platelet count; blood clotting tests: prothrombin time (PT), activated partial thromboplastin time (aPTT)
 - Biochemistry: CMP - glucose, calcium, albumin, total protein, sodium, potassium, CO₂, chloride, BUN, creatinine, total bilirubin, alanine aminotransferase (ALT), aspartate aminotransferase (AST), alkaline phosphatase (ALP), lactate dehydrogenase (LDH); thyroid tests: (TSH and FT4)
 - Urinalysis: UA with microscopic evaluation
 - Serum pregnancy test
 - Anti-double-stranded DNA (anti-dsDNA) antibody test
 - Anti-DNase B Titer, Serum
 - 40 mL of blood will be collected for research purposes in the laboratory of [name], including immune response evaluation.
- Tumor sample biopsy of injected lesion for histology and immune response assays
- Biopsy of non-target lesion (if applicable)
- Assessment and recording of ECOG Performance Status
- Assessment and recording of Tumor Burden (lesion measurements)
- Assessment and recording of Concomitant Medications
- Observation and recording of adverse or serious adverse events as defined by CTCAE v5.0
- CT as clinically indicated and/or PET scan (photographs may be utilized for melanoma confined to the skin)

Overall Survival Status: Long Term Follow-up

- On 11/16/2020 (\pm 4 weeks), the survival status and subsequent anti-cancer therapy since last being seen on trial will be obtained from the EMR. Subsequent therapies will be documented from the EMR for melanoma (immune-based therapy, chemotherapy, radiation, surgery) with clinical response if available.

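### PFS is censored for patients who leave after Week 4 but followed for those who continue, and the plan does not say how off-study progression times will be used (minor)

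*Combined protocol and SAP*

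**What the plan says.** **PFS after the four-week period.** Section 7.1.2 moves patients to standard of care or other trials once the four-week assessments are done. It then states: "If the patient comes off study, PFS will need to be censored, but the time to first progression will be obtained during subsequent follow-up". That collection is subject to the patient's consent. The section continues: "If the patient has a response to therapy, the patient will have the option of continuing the study at three-week intervals". This is left to the PI, who consults the sponsor. For such patients the section adds: "In this setting, PFS will be measured in the traditional way".

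**Who may continue.** Section 4.1 gives the "option of continuing the study at three-week intervals so long as the subject under study has not progressed". In the Protocol Summary (Optional dosing) and section 6.1.9, once the DLT endpoint is met, "patients may receive additional doses on a 3-week cycle". The Study Procedures row of the Summary says: "After the primary endpoint has been met (DLT), patients may receive additional doses on an optional 3-week cycle".

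**Censoring in the statistical section.** Section 10.4.1 censors at last contact, but only patients who are lost or drop out before the Final Study Visit. For a single-dose patient that visit is Week 4 (section 7.3.4).

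**Long-term follow-up.** The Protocol Summary has: "Obtain OS/subsequent treatments for melanoma after MCC 19500 as of 11/16/2020 for all patients with clinical response if available". Section 7.3.4 says that "the survival status and subsequent anti-cancer therapy since last being seen on trial will be obtained from the EMR", with clinical response where available. Both schedule tables in section 7.3.7 also tick medical history in the long-term column. None of these places names a date of progression.

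**Role of PFS.** Section 4.2.2 says PFS will be recorded but that the study's conclusion does not depend on it. Section 10.4.1 calls the analysis largely descriptive.

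**The concern.** Under section 7.1.2, whether a patient is followed for PFS beyond Week 4 can depend on response. A Kaplan-Meier summary assumes that a censored patient has the same future risk as those still followed. Here the patients censored at about Week 4 would tend to be those without a response, and those still at risk would tend to be responders. If responders progress later, the summary is too high.

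The rest of the plan does not settle this. The rule in section 10.4.1 does not reach a patient who completes Week 4 and then leaves. No part of section 10 says whether the off-study progression time in section 7.1.2 counts as a PFS event, is reported separately or is left unused. With six patients, one continuing responder could determine most of any PFS result after Week 4.

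**Working it through.** **1. The plan's own figures.** The plan gives no PFS rate, event count or precision. Its one computed figure is the upper limit in section 10.5 for no DLT in six patients: 1 − 0.05^(1/6) = 0.393, which reproduces. PFS does not enter it.

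**2. Who is followed after Week 4.**

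| Place | Condition for continuing | Discretion stated |
|---|---|---|
| Section 7.1.2 | response | yes |
| Section 4.1 | not progressed | yes |
| Summary (Optional dosing); section 6.1.9 | DLT endpoint met | yes |
| Summary (Study Procedures) | DLT endpoint met | no |

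The bias depends on the share q of progression-free non-responders who leave at Week 4. The documents do not fix q.

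**3. Six assumed patients.** One progresses at Week 4. Three leave progression-free at Week 4 and progress off study at Weeks 8, 10 and 14. Two responders continue and progress at Weeks 20 and 30.

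- Censored at Week 4: S(4) = 5/6. At Week 20 two patients are at risk, so S = 5/6 × 1/2 = 0.42. The median is 20 weeks and 26-week PFS is 0.42.
- With off-study dates: the median is 10 weeks (first time S is at or below 0.5) and 26-week PFS is 1/6 = 0.17.

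**4. Average effect at Week 16.** All inputs are assumed, and Week 16 is not a time point in the plan. There are r responders among six. Non-responder PFS is exponential with median m weeks. Responder PFS is 4 weeks plus an exponential time with median M. Progression by Week 4 counts as an event. If all progression-free non-responders leave (q = 1):

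- censored estimate = [(r + (6 − r) × 0.5^(4/m)) / 6] × 0.5^(12/M)
- full follow-up = [(6 − r) × 0.5^(16/m) + r × 0.5^(12/M)] / 6

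For r = 1, m = 8, M = 76:

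- censored: [(1 + 5 × 0.7071)/6] × 0.896 = 0.678
- full: (5 × 0.25 + 0.896)/6 = 0.358
- difference: 0.320

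The q = 0.5 column comes from simulation under the same model (200,000 trials per case, simulation SE at most 0.001).

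| m, M (weeks), r = 1 | q = 0 | q = 0.5 | q = 1 |
|---|---|---|---|
| 8, 8 | 0 | 0.00 | 0.00 |
| 8, 16 | 0 | 0.036 | 0.142 |
| 8, 76 | 0 | 0.081 | 0.320 |

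The overstatement is zero if nobody leaves, or if both groups have the same hazard after Week 4. Otherwise it is upward whenever responders progress later.

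**The case against.** The strongest reply is that the biased quantity is not planned. The plan specifies no PFS curve, median or landmark, section 10.4.1 does not name PFS among the secondary endpoints, and with six patients the times could simply be listed. This stands, and it is why the point is minor. It does not remove the point, because section 7.1.2 still states a rule for recording PFS, and that rule would bias any summary beyond Week 4.

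Second, section 7.1.2 is open about the censoring and undertakes to obtain time to first progression. This also stands in part. What is missing is how that time is used, and a named place to record it. A reader might infer that off-study progression will go uncollected. The documents do not support that: the follow-up in section 7.1.2 is not said to be limited to the dated record review, and that review includes medical history and clinical response where available, which might capture a date.

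Third, a reader might infer that only responders continue, so that the bias is certain and large. Section 7.1.2 gives responders the option without saying that nobody else has it, and the other statements do not require a response. The opposite inference, that section 4.1 keeps every non-progressor on study and so removes the bias, fails too, because continuation there is also discretionary.

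**Conclusion.** The point holds as a minor one. If PFS beyond Week 4 is summarised under section 7.1.2, the result describes mainly the continuing patients, and it is too high if they progress later than those who leave. The size is unknown. In the illustration with one responder it runs from 0 to 0.32 at Week 16, and every median and leaving share behind that range is an assumption. The direction also rests on responders progressing later, which is plausible but not given in the documents.

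A reader might infer that the trial's conclusions are at risk. They are not: the DLT, feasibility and response-rate results do not depend on this rule.

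**What to change.** Add the date of first progression to the long-term record review already planned, within the consent condition of section 7.1.2. In section 10, state that for all dosed patients the report will list time from Day 0 to first progression or death, on or off study, beside the version censored at off-study, with the start of any later therapy flagged. If off-study dates cannot be obtained, report Week-4 progression status and individual times only, with no PFS curve or median.

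The cost is a few sentences of wording and one extra data item. The downside is that off-study times include later therapy and assessments on no set schedule, which is the reason to show both versions.

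Separately, the statements on who may continue (Protocol Summary, sections 4.1, 6.1.9 and 7.1.2) differ and must be reconciled. Which of them should govern is not a matter for this review.

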7.2 Laboratory Procedures/Evaluations

7.2.1 Clinical Laboratory Evaluations

- Hematology: (Complete Blood Count - CBC) hemoglobin, hematocrit, white blood cells (WBC) with differential count, platelet count, blood clotting tests; prothrombin time (PT) and activated partial thromboplastin time (aPTT)
- Biochemistry (Comprehensive Metabolic Profile - CMP): glucose, calcium, albumin, total protein, sodium, potassium, CO₂, chloride, BUN, creatinine, total bilirubin, alanine aminotransferase (ALT), aspartate aminotransferase (AST), alkaline phosphatase (ALP), lactate dehydrogenase (LDH), Thyroid tests (TSH and FT4)
- Urinalysis: UA with microscopic evaluation
- Serum pregnancy test, done within 24 hours prior to Investigational Product administration, and results must be available prior to administration of Investigational Product
- Human leukocyte antigen (HLA) typing

- Serology screening for HBV, HCV, HIV, HTLV, EBV and *T. pallidum* (RPR); fluorescent treponemal antibody absorption (FTA-ABS), if necessary
- Immunodeficiency Panel
- Anti-double-stranded DNA (anti-dsDNA) antibody test
- Anti-DNase B Titer, Serum

7.3 Study Schedule

7.3.1 Screening

Screening Visit (Day -36 to -1)

- Obtain informed consent of potential participant verified by signature on study informed consent form.
- Verify inclusion/exclusion criteria.
- Review medical history to determine eligibility based on inclusion/exclusion criteria.
- Review medications history to determine eligibility based on inclusion/exclusion criteria.
- Record Concomitant Medications.
- Perform medical examinations needed to determine eligibility based on inclusion/exclusion criteria.
- CT as clinically indicated and/or PET scan. Photographs may be utilized for melanoma confined to the skin.
- Electrocardiogram (ECG)
- Collect blood/urine for:
 - Hematology: CBC - hemoglobin, hematocrit, white blood cells (WBC) with differential count, platelet count; blood clotting tests: prothrombin time (PT) and activated partial thromboplastin time (aPTT)
 - Biochemistry: CMP - glucose, calcium, albumin, total protein, sodium, potassium, CO₂, chloride, BUN, creatinine, total bilirubin, alanine aminotransferase (ALT), aspartate aminotransferase (AST), alkaline phosphatase (ALP), lactate dehydrogenase (LDH), Thyroid tests (TSH and FT4)
 - Urinalysis: UA with microscopic evaluation
 - Serum pregnancy test: done within 24 hours prior to Investigational Product administration, and results must be available prior to Investigational Product administration
 - Human leukocyte antigen (HLA) typing
 - Serology screening for HBV, HCV, HIV, HTLV, EBV and *T. pallidum* (RPR); fluorescent treponemal antibody absorption (FTA-ABS), if necessary
 - Immunodeficiency Panel
 - Anti-double-stranded DNA (anti-dsDNA) antibody test
 - Anti-DNase B Titer, Serum
- Where feasible, as determined by PI, research study biopsy for histology and/or immune response assays may be collected at the screening visit or the baseline visit. PI may also elect to use archival tumor at baseline.

- In the setting of known melanoma, archival tumor tissue may be utilized to confirm the diagnosis (Moffitt or from external source).
- In this case, two 4-micron slices (positive charged slides, air dry overnight). are required for research IHC experiments under the direction of [name].
- The H&E stained slide from the biopsy may be digitally scanned.
- For all portions of this protocol, fresh research biopsies will be obtained using a punch or shave biopsy technique. These samples will be placed in PBS or formalin and utilized for research purposes. The portion of the tissue divided for the PBS portion will be flash frozen and utilized for downstream assays. [name] will assess whether the tumor is of adequate size to split into two parts (PBS and formalin).
- Assessment and recording of ECOG Performance Status.
- Assessment and recording of Tumor Burden (lesion measurements).
- Schedule study visits for participants who are eligible and available for the duration of the study.
- Provide participants with general study procedures and instructions for clinical visits

